### 3.2.2. Secondary Endpoints

#### Immunogenicity

- 50% neutralizing antibody (NT50) geometric mean titer (GMT) against SARS-CoV-2 pseudovirus at baseline, 28 days after the first vaccination and 14 days and 6 months after the second vaccination in all the subjects. The primary analysis will be conducted separately for those who are anti-S IgG seronegative at baseline (no pre-screening for SARS-CoV-2 will be carried out)
- Geometric mean fold rise (GMFR) (from baseline) in NT50 against SARS-CoV-2 pseudovirus at 28 days after the first vaccination, and 14 days and 6 months after the second vaccination
- Percentage of subjects with NT50 seroresponses against SARS-CoV-2 pseudovirus as defined by (1) a  $\geq 4$ -fold increase from baseline, and (2) a  $\geq 10$ -fold increase from baseline at 28 days after the first vaccination and 14 days and 6 months after the second vaccination
- Anti-S IgG GMT at baseline and at 28 days after the first vaccination and 14 days and 6 months after the second vaccination
- GMFR (from baseline) in anti-S IgG GMT at 28 days after the first vaccination and 14 days and 6 months after the second vaccination
- Percentage of subjects with seroresponses in anti-S IgG titer as defined by (1) a  $\geq 4$ -fold increase from baseline, and (2) a  $\geq 10$ -fold increase from baseline, at

28 days after the first vaccination and 14 days and 6 months after the second vaccination

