## 9. IMMUNOGENICITY

The analysis of immunogenicity will be performed on the per protocol population as the primary analysis and the full analysis population as a secondary analysis. Analyses described below will be summarized in the interim analyses for all subjects included in the first phase of the study. Relative endpoints derived from Geometric Mean Fold Rise (GMFR) will include all subjects from the per protocol population. Absolute endpoints such as those derived from the Geometric Mean Titer (GMT) will exclude baseline seropositive subjects (i.e., subjects with anti-S IgG antibody titer  $\geq$  LLOQ of the assay at baseline).

Immunogenicity data will be descriptively summarized including the mean, SD, median, range (min and max), GMT, and 95% CI for the GMT with one-half the lower limit of quantification (LLOQ) and with the upper limit of quantification (ULOQ) used as the observed value, whenever these limits are met. For estimation of the GMT, GMT ratio, and corresponding confidence limits, analyses will incorporate censoring where appropriate and log-scale coefficients will be back-transformed in order to compute the estimate and corresponding confidence limits for the relevant quantity. GMFRs will be computed using estimates of the log difference of the paired samples, with corresponding CIs computed via the *t*-distribution, utilizing the antilog transformation to present the ratio. Analyses of binary variables will include 95% CIs computed via the Clopper-Pearson method. Additionally, the distribution of the titers will be summarized using reverse cumulative distribution curves. ([Figure 27](#) through [Figure 32](#)).

The immunogenicity analysis part will be summarized in term of GMT ratio comparing between dose levels and dose with and without adjuvant. The comparing doses of GMT ratio (95% CI) will be performed for the following pairwise: (1) NDV-HXP-S 1  $\mu$ g vs. 3  $\mu$ g, (2) 1  $\mu$ g vs. 10  $\mu$ g, (3) 3  $\mu$ g vs. 10  $\mu$ g, (4) 1  $\mu$ g vs. 1  $\mu$ g+CPG, (5) 3  $\mu$ g vs. 1  $\mu$ g+CPG, (6) 10  $\mu$ g vs. 1  $\mu$ g+CPG.

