### 9.1. NT50 and NT80 against SARS-CoV-2 Pseudovirus

The pseudovirus neutralization assay (PNA) will be used to quantify the functional humoral immune response against SARS-CoV-2 by measuring the 50% and 80% neutralizing titer (NT50 and NT80) against a SARS-CoV-2 pseudovirus.

The results generated from the central laboratory (NEXELIS, Canada) for SARS-CoV-2 PNA will be reported with titer units “NT50” and “NT80”. A correlation factor of 1/1.872 will be applied to convert the reported results from NT50 titer to IU/mL which is the assigned unit for WHO International Standard.

The following formula shall be used for converting NT50 titer to IU/mL:

$$\text{Result (IU/mL)} = \text{Result (NT}_{50} \text{ titer)} / 1.872$$

The NT50 and NT80 GMT against SARS-CoV-2 pseudovirus will be described along with its 95% CI at baseline (D1), 28 days after the first vaccination (D29), and 14 days (D43) and 6 months (D197) after the second vaccination in subjects who are anti-S IgG seronegative (i.e., anti-S IgG value less than LLOQ of the assay) at baseline ([Table 90](#), [Table 91](#), [Table 94](#), [Table 95](#), Appendix 1). The NT50 will also be described via the geometric mean concentration (GMC) in IU/mL along with its 95% CI at D1, D29, D43 and D197.

The GMT ratio with 95% CI for pairwise comparison of NT50 and NT80 GMT values between dose levels and dose with and without adjuvant will be presented at 28 days after the first vaccination, and 14 days, 6 months and 12 months after the second vaccination for each pair ([Table 92](#), [Table 93](#), [Table 96](#), [Table 97](#)).

The GMFR from baseline in NT50 and NT80 against SARS-CoV-2 pseudovirus at 28 days after the first vaccination, and 14 days, 6 months and 12 months after the second vaccination will be calculated along with its 95% CI for each study group ([Table 98](#) through [Table 101](#), Appendix 1).

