## Appendix 1.J. Immunogenicity Analysis – Anti-S IgG Assessed by ELISA

**Table 110: Summary of Geometric Mean Concentration (GMC) in BAU/mL of Anti-S IgG assessed by ELISA in Full Analysis Population**

Anti-S IgG Measure (BAU/mL)	All (N = 120)	COVIVAC				Placebo (N = 20)
		1 µg (N = 25)	3 µg (N = 25)	10 µg (N = 25)	1 µg + CpG (N = 25)	
Baseline (D1)	GMC (95% CI)					
28 days after the first vaccination (D29)	GMC (95% CI)					
14 days after the second vaccination (D43)	GMC (95% CI)					
6 months after the second vaccination (D197)	GMC (95% CI)					

**Note:** GMCs are analyzed from subjects with seronegative anti-S IgG at baseline.

**Table 110-1: Summary of Geometric Mean Concentration (GMC) in BAU/mL of Anti-S IgG assessed by ELISA in Full Analysis Population by Age Group**

Anti-S IgG Measure (BAU/mL)	All (N = 120)	COVIVAC				Placebo (N = 20)
		1 µg (N = 25)	3 µg (N = 25)	10 µg (N = 25)	1 µg + CpG (N = 25)	
Baseline (D1)	18-39 yr.	GMC (95% CI)				
	40-59 yr.	GMC (95% CI)				
28 days after the first vaccination (D29)	18-39 yr.	GMC (95% CI)				
	40-59 yr.	GMC (95% CI)				
14 days after the second vaccination (D43)	18-39 yr.	GMC (95% CI)				
	40-59 yr.	GMC (95% CI)				
6 months after the second vaccination (D197)	18-39 yr.	GMC (95% CI)				
	40-59 yr.	GMC (95% CI)				

**Note:** GMCs are analyzed from subjects with seronegative anti-S IgG at baseline.

**Table 110-2: Summary of Geometric Mean Concentration (GMC) in BAU/mL of Anti-S IgG assessed by ELISA in Full Analysis Population by Gender**

Anti-S IgG Measure (BAU/mL)	All (N = 120)	COVIVAC				Placebo (N = 20)
		1 µg (N = 25)	3 µg (N = 25)	10 µg (N = 25)	1 µg + CpG (N = 25)	
Baseline (D1)	Male	GMC (95% CI)				
	Female	GMC (95% CI)				
28 days after the first vaccination (D29)	Male	GMC (95% CI)				
	Female	GMC (95% CI)				
14 days after the second vaccination (D43)	Male	GMC (95% CI)				
	Female	GMC (95% CI)				
6 months after the second vaccination (D197)	Male	GMC (95% CI)				
	Female	GMC (95% CI)				

**Note:** GMCs are analyzed from subjects with seronegative anti-S IgG at baseline.

**Table 111: Summary of Geometric Mean Concentration (GMC) in BAU/mL of Anti-S IgG assessed by ELISA in Per Protocol Population**

Anti-S IgG Measure (BAU/mL)	All (N = 120)	COVIVAC				Placebo (N = 20)
		1 µg (N = 25)	3 µg (N = 25)	10 µg (N = 25)	1 µg + CpG (N = 25)	
Baseline (D1)	GMC (95% CI)					
28 days after the first vaccination (D29)	GMC (95% CI)					
14 days after the second vaccination (D43)	GMC (95% CI)					

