6 months after the second vaccination (D197)	GMC (95% CI)					

**Note:** GMCs are analyzed from subjects with seronegative anti-S IgG at baseline.

**Table 111-1: Summary of Geometric Mean Concentration (GMC) in BAU/mL of Anti-S IgG assessed by ELISA in Per Protocol Population by Age Group**

Anti-S IgG Measure (BAU/mL)	All (N = 120)	COVIVAC				Placebo (N = 20)
		1 µg (N = 25)	3 µg (N = 25)	10 µg (N = 25)	1 µg + CpG (N = 25)	
Baseline (D1)	18-39 yr.	GMC (95% CI)				
	40-59 yr.	GMC (95% CI)				
28 days after the first vaccination (D29)	18-39 yr.	GMC (95% CI)				
	40-59 yr.	GMC (95% CI)				
14 days after the second vaccination (D43)	18-39 yr.	GMC (95% CI)				
	40-59 yr.	GMC (95% CI)				
6 months after the second vaccination (D197)	18-39 yr.	GMC (95% CI)				
	40-59 yr.	GMC (95% CI)				

**Note:** GMCs are analyzed from subjects with seronegative anti-S IgG at baseline.

**Table 111-2: Summary of Geometric Mean Concentration (GMC) in BAU/mL of Anti-S IgG assessed by ELISA in Per Protocol Population by Gender**

Anti-S IgG Measure (BAU/mL)	All (N = 120)	COVIVAC				Placebo (N = 20)
		1 µg (N = 25)	3 µg (N = 25)	10 µg (N = 25)	1 µg + CpG (N = 25)	
Baseline (D1)	Male	GMC (95% CI)				
	Female	GMC (95% CI)				
28 days after the first vaccination (D29)	Male	GMC (95% CI)				
	Female	GMC (95% CI)				
14 days after the second vaccination (D43)	Male	GMC (95% CI)				
	Female	GMC (95% CI)				
6 months after the second vaccination (D197)	Male	GMC (95% CI)				
	Female	GMC (95% CI)				

**Note:** GMCs are analyzed from subjects with seronegative anti-S IgG at baseline.

**Table 112: Summary of Geometric Mean Concentration Ratio (GMC Ratio) of Anti-S IgG assessed by ELISA in Full Analysis Population**

Anti-S IgG GMC ratio (95% CI)	COVIVAC					
	1 µg vs 3 µg	1 µg vs 10 µg	3 µg vs 10 µg	1 µg vs 1 µg + CpG	3 µg vs 1 µg + CpG	10 µg vs 1 µg + CpG
Baseline (D1)						
28 days after the first vaccination (D29)						
14 days after the second vaccination (D43)						
6 months after the second vaccination (D197)						

**Note:** Anti-S IgG GMCs are analyzed from subjects with seronegative anti-S IgG at baseline.

**Table 112-1: Summary of Geometric Mean Concentration Ratio (GMC Ratio) of Anti-S IgG assessed by ELISA in Full Analysis Population by Age Group**

Anti-S IgG GMC ratio (95% CI)	COVIVAC					
	1 µg vs 3 µg	1 µg vs 10 µg	3 µg vs 10 µg	1 µg vs 1 µg + CpG	3 µg vs 1 µg + CpG	10 µg vs 1 µg + CpG
Baseline (D1)	18-39 yr. 40-59 yr.					

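### The Baseline (D1) rows of the anti-S IgG GMC and GMC-ratio tables (Tables 110 to 113-2) are fixed by their own selection rule, so baseline anti-S IgG is not informatively estimated

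*SAP*

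**What the plan says.** - **Endpoint.** Section 3.2.2 lists "Anti-S IgG GMT at baseline and at 28 days after the first vaccination" as a secondary endpoint, with later time points. The bullet carries no serostatus restriction; the sentence about seronegative subjects belongs to the NT50 bullet. That same NT50 bullet says subjects are not pre-screened for SARS-CoV-2.
- **Exclusion.** Section 9 states that absolute endpoints "will exclude baseline seropositive subjects", meaning those at or above the LLOQ, and makes no exception for the baseline time point. Section 9.1 defines the retained set as those "who are anti-S IgG seronegative (i.e., anti-S IgG value less than LLOQ of the assay) at baseline".
- **Values below LLOQ.** Section 9 summarises immunogenicity data "with one-half the lower limit of quantification (LLOQ) and with the upper limit of quantification (ULOQ) used as the observed value". Its next sentence brings censoring into the estimation of GMTs and ratios where that is suitable.
- **Shells.** Tables 110 to 111-2 (GMC) have a Baseline (D1) row and the note "GMCs are analyzed from subjects with seronegative anti-S IgG at baseline". Tables 112 to 113-2 (six pairwise ratios) also have that row and the note "Anti-S IgG GMCs are analyzed from subjects with seronegative anti-S IgG at baseline".
- **Baseline in the text.** Section 9.2 asks for GMTs at baseline but does not attach baseline to the ratio. For NT50 and NT80, section 9.1 lists ratio time points only from day 29 onward.
- **Relative endpoints.** Section 9 keeps all per-protocol subjects in the GMFR analyses, and the seroresponse shells carry no seronegative note.

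**The concern.** The filter and the outcome are the same day 1 result. Once everyone at or above the LLOQ has been removed, nothing remains for the baseline row to estimate. A stated secondary endpoint is left without a usable result in either population.

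The information lost is useful. Seropositive subjects can be enrolled, and they contribute to the fold-rise and seroresponse results, which are measured against each subject's own baseline. A reader of those tables would want to know how many subjects in each arm started with measurable antibody, and no shell says so directly. Table 28 covers only HBsAg and HCV Ab.

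**Working it through.** **Inputs from the SAP.** The retained set is baseline anti-S IgG < LLOQ (sections 9 and 9.1). The substituted value is LLOQ/2 (section 9). The conversion is BAU/mL = ELU/mL / 7.9815 (section 9.2). There are 25 subjects per active arm. The SAP prints no expected figure for these rows, so there is none to reproduce. It also gives no ELISA LLOQ, so 10, 50 and 100 ELU/mL are assumed to show the range.

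**Step 1: half-LLOQ rule.** Each retained value is c = (LLOQ/2)/7.9815.

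- LLOQ 10: 5/7.9815 = 0.626 BAU/mL
- LLOQ 50: 25/7.9815 = 3.132 BAU/mL
- LLOQ 100: 50/7.9815 = 6.264 BAU/mL

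The mean of identical logs is ln c and their SD is 0. With n ≥ 2 the GMC is therefore c with 95% CI (c, c). With n = 1 there is no t-interval, and with n = 0 there is no GMC. For any two arms the ratio is c/c = 1.00 (1.00-1.00). The assumed LLOQ changes c but not the ratio.

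**Step 2: censored estimation.** With all n values left-censored, the log-likelihood is n × ln Φ((ln LLOQ − μ)/σ). For n = 25, σ = 1 and LLOQ = 10:

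| μ | log-likelihood |
|---|---|
| 1 | −2.53 |
| 0 | −0.27 |
| −2 | −0.0002 |

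It rises towards its bound of 0 as μ falls and never reaches a maximum, so there is no finite estimate.

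**Step 3: what the restriction can conceal (illustration only).** Assume seropositive subjects sit at 20 × LLOQ, which is 40 times the substituted value (ln 40 = 3.689). In all subjects, the log ratio of two arms of 25 is (k1 − k2)/25 × 3.689, where k is the number seropositive. Intervals use the pooled-variance t method.

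| Seropositive, arm 1 vs arm 2 | All-subject ratio (95% CI) | Ratio in seronegatives only |
|---|---|---|
| 1/25 vs 5/25 | exp(−0.590) = 0.55 (0.28-1.09) | 1.00 (1.00-1.00) |
| 0/25 vs 8/25 | exp(−1.180) = 0.31 (0.15-0.62) | 1.00 (1.00-1.00) |

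The SAP gives no seropositivity rate, so the counts and the 20-fold level are assumptions.

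**Step 4: extent.** Tables 110, 111, 112 and 113, each with an age and a gender version, make 4 × 3 = 12 tables. The NT50 and NT80 baseline rows do not share the defect, because their subjects are selected on a different assay.

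**The case against.** The strongest reply is that the restriction is openly stated. Every affected table carries the note, and a reader who sees 1.00 (1.00-1.00) beneath it should understand that all retained values were below the LLOQ. That stands. A reader might infer that the tables assert balance between the randomised arms, but with the note in place they make no such claim.

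A second tempting inference is that these rows could distort down-selection. The documents do not support it. Sections 4.1 and 5 rest advancement on the day 43 NT80 four-fold seroresponse (lower limit at least 52%), ranking of group means, safety and sponsor considerations. None of these uses baseline anti-S IgG.

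Third, the number excluded is partly visible. Table 90A has a place for n at baseline under an arm heading that gives N. However, N minus n mixes seropositive subjects with missing results, and Tables 110 to 113-2 show no n. Listing 13 gives individual values by visit, and Figures 31-32 plot anti-S IgG distributions (the plots are not available here). Section 6.6.1 puts neither in the interim report, which does include Tables 90-119, so they help only at the final analysis.

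Fourth, censoring is to be used only where suitable, so the analyst may fall back on LLOQ/2. That is reasonable, but it leads back to the constant.

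Finally, history of laboratory-confirmed COVID-19 is an exclusion criterion, so seropositive subjects may be few. That limits the consequence but does not make the row informative.

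**Conclusion.** The point holds as a reporting error of minor severity: the Baseline (D1) rows of 12 tables are wrong as written. Their content is set by the selection rule, being LLOQ/2 and 1.00 under substitution and not estimable under censoring. This follows from the SAP's own definitions and needs no assumption about the LLOQ. It requires only at least two retained subjects per cell for an interval to be printed.

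Two consequences follow. The baseline anti-S IgG endpoint of section 3.2.2 is not informatively estimated, and baseline seropositivity by arm is never tabulated explicitly. How much imbalance could go unseen cannot be stated from the document, since the ratios of 0.55 and 0.31 above rest on assumed counts and levels.

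Post-vaccination GMCs, fold rises, seroresponse rates and the advancement rule are unchanged. A reader might also conclude that the seronegative restriction is itself mistaken. It is not: for post-vaccination rows it is coherent and should stay.

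**What to change.** 1. In Tables 110 and 111 and their age and gender versions, compute the Baseline (D1) row in all subjects of the population concerned. Add n (%) at or above LLOQ per arm, and the quartiles.
2. Delete the Baseline (D1) row from Tables 112 and 113 and their age and gender versions. This agrees with section 9.2, which does not ask for a baseline ratio.
3. Reword the notes so that the seronegative restriction applies to post-vaccination rows only, and add a sentence to that effect in section 9 or 9.2.

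The cost is a change to shell notes and a sentence of text, with the matching table programming. The baseline samples and results are already planned, so no new data are needed.

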## Appendix 1.L. Concomitant Medication

**Table 120: Concomitant Medication by Pharmacological Class According to WHO DD**

[figure not shown]
Anatomical Main Group	Therapeutic Subgroup	All (N = 120)	COVIVAC				Placebo (N = 20)
			1 µg (N = 25)	3 µg (N = 25)	10 µg (N = 25)	1 µg + CpG (N = 25)	
All		xx (xx.x%)	xx (xx.x%)	xx (xx.x%)	xx (xx.x%)	xx (xx.x%)	xx (xx.x%)
ATC 1		xx (xx.x%)	xx (xx.x%)	xx (xx.x%)	xx (xx.x%)	xx (xx.x%)	xx (xx.x%)
ATC 2		xx (xx.x%)	xx (xx.x%)	xx (xx.x%)	xx (xx.x%)	xx (xx.x%)	xx (xx.x%)
ATC 3		xx (xx.x%)	xx (xx.x%)	xx (xx.x%)	xx (xx.x%)	xx (xx.x%)	xx (xx.x%)

**Note:** Number of subject with at least one concomitant medication in a given pharmacological class

**Appendix 2.A.****Demographics****Figure 1: Consort Diagram**

**Appendix 2.B.****Laboratory Values****Figure 2: Hemoglobin (g/dL) from Baseline Across Visit by Vaccination Groups**

[figure not shown]
Mock data was used to prepare the dummy plot.

**Figure 3: White Blood Cell (WBC) ( $\times 10^3/\mu\text{L}$ ) from Baseline Across Visit by Vaccination Groups****Figure 4: Platelets ( $\times 10^3/\mu\text{L}$ ) from Baseline Across Visit by Vaccination Groups****Figure 5: Creatinine (mg/dL) from Baseline Across Visit by Vaccination Groups****Figure 6: ALT (U/L) from Baseline Across Visit by Vaccination Groups****Figure 7: AST (U/L) from Baseline Across Visit by Vaccination Groups****Figure 8: Total Bilirubin (mg/dL) from Baseline Across Visit by Vaccination Groups**

[figure not shown]
Box and whisker plot will be presented for all laboratory results.

## Appendix 2.C. Immunogenicity - Geometric Mean Titer (GMT), Geometric Mean Fold Rise (GMFR)

**Figure 9: Geometric Mean Titer (GMT), Geometric Mean Fold Rise (GMFR) of NT50 against SARS-CoV-2 Pseudovirus in Full Analysis Population**

Bars represent geometric mean titer and 95% CI

Bars represent geometric mean fold-rise (GMFR) and 95% CI

[figure not shown]
**Figure 10: Geometric Mean Titer (GMT), Geometric Mean Fold Rise (GMFR) of NT50 against SARS-CoV-2 Pseudovirus in Per Protocol Analysis Population**

**Figure 11: Geometric Mean Titer (GMT), Geometric Mean Fold Rise (GMFR) of NT80 against SARS-CoV-2 Pseudovirus in Full Analysis Population**

**Figure 12: Geometric Mean Titer (GMT), Geometric Mean Fold Rise (GMFR) of NT80 against SARS-CoV-2 Pseudovirus in Per Protocol Analysis Population**

**Figure 13: Geometric Mean Concentration (GMC), Geometric Mean Fold Rise (GMFR) of Anti-S IgG assessed by ELISA in Full Analysis Population**

**Figure 14: Geometric Mean Concentration (GMC), Geometric Mean Fold Rise (GMFR) of Anti-S IgG assessed by ELISA in Per Protocol Analysis Population**

**Appendix 2.D.****Immunogenicity - Seroresponses****Figure 15: NT50 Seroresponses against SARS-CoV-2 Pseudovirus as defined by a  $\geq 4$ -fold Increase from Baseline in Full Analysis Population****Figure 16: Percentage of Subjects with NT50 Seroresponses against SARS-CoV-2 Pseudovirus as defined by a  $\geq 4$ -fold Increase from Baseline in Per Protocol Analysis Population****Figure 17: Percentage of Subjects with NT80 Seroresponses against SARS-CoV-2 Pseudovirus as defined by a  $\geq 4$ -fold Increase from Baseline in Full Analysis Population****Figure 18: Percentage of Subjects with NT80 Seroresponses against SARS-CoV-2 Pseudovirus as defined by a  $\geq 4$ -fold Increase from Baseline in Per Protocol Analysis Population****Figure 19: Percentage of Subjects with NT50 Seroresponses against SARS-CoV-2 Pseudovirus as defined by a  $\geq 10$ -fold Increase from Baseline in Full Analysis Population****Figure 20: Percentage of Subjects with NT50 Seroresponses against SARS-CoV-2 Pseudovirus as defined by a  $\geq 10$ -fold Increase from Baseline in Per Protocol Analysis Population**

**Figure 21: Percentage of Subjects with NT80 Seroresponses against SARS-CoV-2 Pseudovirus as defined by a  $\geq$  10-fold Increase from Baseline in Full Analysis Population**

[figure not shown]
**Figure 22: Percentage of Subjects with NT80 Seroresponses against SARS-CoV-2 Pseudovirus as defined by a  $\geq$  10-fold Increase from Baseline in Full Analysis Population**

**Figure 23: Percentage of Subjects with Seroresponses in Anti-S IgG Concentration (BAU/mL) assessed by ELISA as defined by a  $\geq$  4-fold Increase from Baseline in Full Analysis Population**

**Figure 24: Percentage of Subjects with Seroresponses in Anti-S IgG Concentration (BAU/mL) assessed by ELISA as defined by a  $\geq$  4-fold Increase from Baseline in Per Protocol Analysis Population**

**Figure 25: Percentage of Subjects with Seroresponses in Anti-S IgG Concentration (BAU/mL) assessed by ELISA as defined by a  $\geq$  10-fold Increase from Baseline in Full Analysis Population**

**Figure 26: Percentage of Subjects with Seroresponses in Anti-S IgG Concentration (BAU/mL) assessed by ELISA as defined by a  $\geq$  10-fold Increase from Baseline in Per Protocol Analysis Population**

**Appendix 2.E.****Immunogenicity – Reverse Cumulative****Figure 27: NT50 Titer Seroresponses against SARS-CoV-2 Pseudovirus Reverse Cumulative Distribution Curves in Full Analysis Population**

**Figure 28: NT50 Titer Seroresponses against SARS-CoV-2 Pseudovirus Reverse Cumulative Distribution Curves in Per Protocol Analysis Population**

**Figure 29: NT80 Titer Seroresponses against SARS-CoV-2 Pseudovirus Reverse Cumulative Distribution Curves in Full Analysis Population**

**Figure 30: NT80 Titer Seroresponses against SARS-CoV-2 Pseudovirus Reverse Cumulative Distribution Curves in Per Protocol Analysis Population**

**Figure 31: Anti-S IgG Concentration (BAU/mL) Assessed by ELISA Reverse Cumulative Distribution Curves in Full Analysis Population**

**Figure 32: Anti-S IgG Concentration (BAU/mL) Assessed by ELISA Reverse Cumulative Distribution Curves in Per Protocol Analysis Population**

